Related to the capacity aim, the Community Advisory Board (CAB) includes about 20 local Dan River Region health care and community partners and academic researchers. Some members of the CAB will be responsible for screening, recruit, enrollment/data collection, and program implementation and are included as study investigators. The Parent Advisory Team (PAT) includes about 15 parents who are past iChoose program participants who will serve in a similar role as a community health worker or patient navigator. They will be asked to assist in distributing recruitment materials for our open referral/enrollment process, help potential families understand both programs and timing of the intervention sessions, and ask to promote program adherence and provide a program 'safety net'. This will include contacting enrolled families and supporting their needs to successfully engage in the program. Both the PAT and CAB groups will meet monthly (e.g. using a mix of in-person and conference call meetings) and use a shared-decision making and participatory agenda meeting structure to guide all aspects of the study. As a part of this process, those who volunteer and sign informed consent will also participate in annual mixed-methods evaluation to assess capacity and engagement. Patient and stakeholder engagement and evaluation is a requirement of our funder.

To this end, we have 4 groups of participants who are in this protocol: 1) children, 2) parents of these children, 3) Community Advisory Board (CAB) members, and 4) Parent Advisory Team (PAT) members. Some members of the CAB and PAT, are both involved in the conducting the research and are research subjects who will be completing the mixed-methods evaluation as indicated in the CAB and PAT consent forms [NOTE: PAT members may NOT be simultaneously enrolled at participants in the childhood obesity treatment program].

Background

1. Provide the scientific background, rationale and relevance of this project.

A. Background

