Community Advisory Board members were identified and named when the PCORI application was submitted:

- Representatives from organizations in the Dan River Region who have a child-focused organizational mission, invited as a stakeholder
- ≥18 years of age
- Willing and able to provide informed consent

Parent Advisory Team members:

- Parent who previously participated in a childhood obesity program and/or are the parent of a child ages 5-12 years of age
- ≥18 years of age
- live in the Dan River Region

2. List the criteria for exclusion

Parent/child dyads:

- children with a major cognitive impairment based on medical record review or contraindications for physical activity
- families that are already participating in a childhood obesity treatment program

Community Advisory Board: none

Parent Advisory Team:

- Cannot simultaneously be enrolled in the comparative effectiveness trial and serve on the Parent Advisory Team

3. List any restrictions on use of other drugs or treatments.

Parent/child dyads

- families that are already participating in a childhood obesity treatment program will be excluded

Community Advisory Board and Parent Advisory Team: NA

Statistical Considerations

1. Is stratification/randomization involved?

Yes

► IF YES, describe the stratification/ randomization scheme.

We will use simple randomization, at the parent-child dyad level. Randomization is not blinded. The researchers will have access to the randomization scheme.

► IF YES, who will generate the randomization scheme?

Sponsor
 UVa Statistician. Answer/Response:

UVa Investigational Drug Service (IDS)
 X Other: [name], statistician from Virginia Tech

2. What are the statistical considerations for the protocol?

- The primary end-point is 6-month reduction in BMI z-score.
- We calculated a standardized effect size relative to the differences in BMI z-scores and standard deviations *related to 6-month BMI z-score reduction* for *Family Connections* (0.07) and *Bright Bodies* as a target for the *iChoose+* condition (BMI z-score reduction = 0.16).

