APPENDIX: Legal/Regulatory

Recruitment

The following procedures will be followed:

Version Date: 04/22/2020

Page Number: 46 of 67

IRB-HSR # 19748: A randomized-controlled trial to compare the reach, effectiveness and maintenance of two family-based childhood obesity treatment programs in a medically underserved region

- Finder's fees will not be paid to an individual as they are not allowed by UVa Policy.
- All recruitment materials will be approved by the IRB-HSR prior to use. They will be submitted to the IRB after the IRB-HSR has assigned an IRB-HSR # to the protocol.
- Only those individuals listed as personnel on this protocol will recruit and or conduct the consenting process with potential subjects.

Retention Incentives

Any item used by the sponsor/ study team to provide incentive to a subject to remain in the study, other than compensation identified in the Payment section, will be submitted to the IRB for review prior to use. The IRB-HSR will provide the study team with a Receipt Acknowledgement for their records. Retention incentive items are such things as water bottles, small tote bags, birthday cards etc. Cash and gift cards are not allowed as retention incentives.

Clinical Privileges

The following procedures will be followed:

- Investigators who are members of the clinical staff at the University of Virginia Medical Center must have the appropriate credentials and been granted clinical privileges to perform specific clinical procedures whether those procedures are experimental or standard.
- The IRB cannot grant clinical privileges.
- Performing procedures which are outside the scope of the clinical privileges that have been granted may result in denial of insurance coverage should claims of negligence or malpractice arise.
- Personnel on this protocol will have the appropriate credentials and clinical privileges in place before performing any procedures required by this protocol.
- Contact the Clinical Staff Office- [name] or [name] for further information.

Sharing of Data/Specimens

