DHHS & HIPAA: Study team requests a Waiver of Consent and a Waiver of HIPAA Authorization to contact potential subjects.

IMPORTANT:

Keep in mind that contacting individuals in a clinical setting may only be performed by individuals who work under the UVa HIPAA covered entity; which means they meet one of the following criteria:

a UVa student working in the UVa HIPAA Covered Entity*
a faculty or staff member in a PAID appointment in the UVA HIPAA Covered Entity*

You should share the following information with the potential subject:

- Your name
- Who you are: physician, nurse etc. at the University of Virginia.
- Why you want to speak with them
- Ask if you have their permission to explain the study to them
- If asked about how you obtained their information use one of the following as an option for response.

- DO NOT USE THIS RESPONSE UNLESS YOU HAVE OBTAINED PERMISSION FROM THEIR UVa PHYSICIAN: Your doctor, Dr. insert name wanted

you to be aware of this research study and gave us permission to contact you.

- We obtained your information from your medical records at UVa.
- Federal regulations allow the UVa Health System to release your information to researchers at UVa, so that we may contact you regarding studies you may be interested in participating. We want to assure you that we will keep your information confidential.

- IF THE PERSON SEEMS ANGRY, HESITANT OR UPSET, THANK THEM FOR THEIR TIME AND DO NOT ENROLL THEM IN THE STUDY. YOU MAY ALSO REFER THEM TO THE IRB-HSR AT [name].

c. Direct contact of potential subjects by the study team by approaching in person at UVa or via letter, phone, direct e-mail. Members of study team contacting potential subjects ARE health care providers of patients. [Note: letter sent to eligible patients from their physician at SOVAH Pediatrics and PATHS. The letter includes information about the projects and makes the parent aware that someone from the study team will call them with more information. They are able to opt out of this call by either calling the contact at SOVAH Pediatrics or PATHS or by sending back the opt out post-card. The opt out postcard is not prestamped. It includes no study identifiers other than the IRB #. First and last name of the parent is requested for opting out.]

If you are not approaching them in person but using a letter, phone call or direct email please note that the letter, phone, direct email scripts must be approved by IRB prior to use. See [IRB-HSR Website](#) for templates.

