Do you confirm that health information with HIPAA identifiers will not be shared outside of UVa until a consent form is signed or only shared in a de-identified manner?

Yes

4. Do you plan to ask the subjects to do anything, other than answering questions, for the study prior to signing a consent?

For example: come to the first visit fasting, stop taking medications that may be an exclusion criteria, change diet. As this is still part of pre-screening one is not allowed to gather information that is not directly related to inclusion/exclusion criteria or other issues of suitability (e.g. is person able to come to UVa for multiple visits)

NOTE:

Only those members of the study team with a DEA# (license to prescribe drugs) are allowed to determine if a potential subject may be asked/informed to stop taking a drug which is an exclusion criteria. It is recommended that the potential subject notify their health care provider if they plan to stop a prescription drug.

Yes

►IF YES, explain in detail what you will ask them to do.

For families who express interest in the study by responding through advertisements or flyers, their child will need to be screened for BMI inclusion criteria. Therefore, the child's height and weight will be taken prior to informed consent to check for study eligibility. In addition, they will answer the study questions similar to families who were identified via the medical record review at SOVAH Pediatrics and PATHS.

Tips to Study Team

You must document their verbal consent in the study records.

If a subject is asked to stop taking a drug, document the date and name of the person on the study team giving the verbal order to stop medications (again- must be a person with a DEA#).

DHHS: Study team requests the use of Verbal Consent (Waiver of Documentation of Consent) for minimal risk screening procedures.

HIPPA:

If the individual, obtaining consent, works under the HIPAA Covered Entity this is covered under Health Care Operations

If the individual obtaining consent does not work under the HIPAA covered entity, HIPAA does not apply.

5. How will the consenting process take place with either the prospective subject, the subject's legally authorized representative or parent/legal guardian of a minor (if applicable)?

HIPPA:

If the individual, obtaining consent, works under the HIPAA Covered Entity consenting is covered under Health Care Operations.

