If the individual obtaining consent does not work under the HIPAA covered entity, HIPAA does not apply.

Describe the setting for the consent process.

If the study is of a sensitive nature and/or includes a reference to a medical condition how will you protect the privacy of the potential subject when they are approached to participate?

Who will discuss the study with the potential subject?

Where will the consenting process take place?

How will you assess subject understanding?

How much time will pass between obtaining written consent and initiation of study procedures?

See Protocol Examples: [Consenting Process](#) for examples of how to answer this question.

If recruiting minors, specify how parental /guardian consent will be obtained prior to approaching the minor.

Answer/Response:

SEE ATTACHMENTS:

1. _consent_parent
2. _minor_assent
3. _consent_CAB
4. _consent_PAT

Parents: sign consent prior to enrolling in the main study and any study procedures.

IRB-HSR # 19748: A randomized-controlled trial to compare the reach, effectiveness and maintenance of two family-based childhood obesity treatment programs in a medically underserved region

Child: assent prior to enrolling in the main study (after parental signed consent is obtained)

The consent/assent process will take place in-person when the families arrive for their enrollment appointment. The consent and assent statements will be read aloud and all questions will be answered. The study procedures will occur the same day as consent. Note, the pre-screening process that occurs 1-3 weeks prior to enrollment also describes the study process and procedures, and a copy of the consent form is provided to the parents to review prior to their enrollment appointment.

Community Advisory Board and Parent Advisory Team: sign consent prior to participating in mixed methods evaluation which will occur at one of the regular meetings. Researchers are available to answer any questions.

6. Will subjects sign a consent form for any part of the study?

Yes

7. Will the study procedures be started the same day the subject is recruited for the study?

Yes

►IF YES, explain in detail why the subject cannot be given more time to make a decision to consent.

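### The plan gives the researchers access to the randomization scheme and does not say that a dyad is assigned only after eligibility, consent and baseline measurement, so as written it permits foreknowledge of the next assignment

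*Combined protocol and SAP*

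**What the plan says.** Statistical Considerations, question 1, specifies simple randomization at the level of the parent-child dyad and continues: "Randomization is not blinded. The researchers will have access to the randomization scheme". The next item names a statistician at Virginia Tech as the person who generates the scheme. It does not mention custody or release.

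Other sections describe who meets families before assignment:

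- Brief Summary/Abstract, on the Community Advisory Board (CAB): "Some members of the CAB will be responsible for screening, recruit, enrollment/data collection, and program implementation and are included as study investigators".
- Appendix: Recruitment, question 2c: for families found by chart review, the physician's letter "makes the parent aware that someone from the study team will call them with more information".
- Appendix: Legal/Regulatory, Recruitment: "Only those individuals listed as personnel on this protocol will recruit and or conduct the consenting process with potential subjects".
- The questions on non-UVA personnel (question 6): Parks and Recreation program leaders may help with telephone screening before consent.

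The order of steps is given in part. Appendix: Recruitment, question 5, says that "the pre-screening process that occurs 1-3 weeks prior to enrollment also describes the study process and procedures". For families who answer advertisements, question 4 says that "the child's height and weight will be taken prior to informed consent to check for study eligibility". On the enrolment visit, question 5 says: "The study procedures will occur the same day as consent". Randomization is not placed anywhere in this sequence.

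**The concern.** Blinding and allocation concealment are separate safeguards. Neither program can be disguised from families or staff, so open-label delivery is unavoidable. Concealing the next assignment until a dyad is irrevocably enrolled remains feasible, and it is what makes the arms comparable at entry.

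A recruiter who can see the next assignment can, without intending to, press harder or less hard for consent, or time an enrolment, according to how well a family seems to suit that program. The two programs differ greatly in demand: 12 family classes and 48 exercise sessions against two parent sessions, plus automated calls in both. A family's apparent readiness is therefore something a recruiter could react to. A person who knows the arm when taking baseline height and weight could also affect the starting value of the primary outcome. Either route would put a bias of unknown direction and size into the 6-month BMI z-score contrast.

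The access sentence is an affirmative statement, which is why this is more than a gap in description.

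**Working it through.** The plan states no figure on this point, so the main check sets the text side by side.

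1. **Who has access.** The researchers (Statistical Considerations, question 1). No role or time limit is given.
2. **Who recruits and enrols.** Listed protocol personnel only (Appendix: Legal/Regulatory), a study team caller (Appendix: Recruitment, question 2c), and some CAB members who count as study investigators (Brief Summary/Abstract). Program leaders may help with telephone screening (non-UVA personnel, question 6). Read in the ordinary way, the researchers overlap with the people who recruit.
3. **Who generates the list.** A statistician at another university. Generation outside the team does not conceal the list if the team is then given it.
4. **Who holds and releases it.** Not stated. No central, sealed or sequential release is described.
5. **When a dyad is assigned.** Not stated. Pre-screening comes 1 to 3 weeks before enrolment, and consent and study procedures fall on one day. Assignment could come before, between or after these steps without contradicting the text.
6. **Other protections.** Biomedical Research, question 1, says that families have an equal chance of either program and cannot choose. That limits families, not what staff know.

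Items 1 and 2 together allow foreknowledge, and nothing in items 3 to 6 rules it out.

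**Could the baseline table show that allocation was concealed?** Statistical Considerations, question 2, plans a baseline comparison between groups. Inputs: n = 87 per arm (Statistical Considerations, question 3), assuming that simple randomization gives an equal split.

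- Standard error of a standardized difference: √(2/n) = √(2/87) = 0.1516 SD.
- 95% half-width: t(0.975; 172 df) × 0.1516 = 1.974 × 0.1516 = 0.299, about 0.30 SD.
- Power of a two-sided 0.05 baseline test: a true imbalance of 0.10 SD (noncentrality 0.10/0.1516 = 0.66) is flagged about 10% of the time. One of 0.20 SD (noncentrality 1.32) is flagged about 26% of the time.

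Imbalances of those sizes would usually pass unnoticed, and the table covers measured variables only. A clean table is therefore no substitute for a record of access and timing.

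**The case against.** The strongest reply is that the text may not mean what it seems to. The form first asks for a description of the randomization scheme, which is the method, and then asks who generates it, which is the list. Access to the *scheme* may therefore mean only that the method is known, and the sentence on blinding may say only that delivery is open-label. Pages have been removed from the public text, and the manual of procedures cited in Statistical Considerations, question 2, is not part of it. Either could hold a safeguard. All of this stands, and it limits the claim to what the plan permits as written.

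Second, no section says that the people who recruit hold the list. That also stands: the overlap lies in roles, and actual sight of the list is not documented. Clinic nurses help with screening at the two practices, and nothing gives them access. A reader might point to the exclusion of "children with a major cognitive impairment based on medical record review or contraindications for physical activity" as leaving room for judgement, but the documents do not show that anyone with access applies it.

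Third, simple randomization cannot be predicted from past assignments. This is true and a real strength, but it protects against guessing, not against reading the list. Likewise, the cohort structure would have made it easy to assign a whole cohort after baseline. The plan does not say that this was done.

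Fourth, it is late. This version is dated 04/22/2020, cohort 3 was planned to start in 2/2019, and the COVID-19 note concerns only cohort 3 data at 12 months. Assignment is almost certainly complete. That moves most of the remedy from procedure to reporting.

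**Conclusion.** The point holds in a limited form. The access sentence, followed as written, permits foreknowledge, and the public text describes no step that prevents it. This is a cheap improvement, not evidence of a flawed result.

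A reader might go further and infer that recruiters saw the list, that assignment preceded baseline, or that enrolment was steered. The documents support none of these. A reader might also take the planned gap between eligible and enrolled dyads as a sign of selection. It is a recruitment forecast, and families' own refusals will explain much of it. Nor do the documents allow a bias or an inflated type I error to be calculated, since any such figure would rest on an assumed imbalance. If assignments were in fact released after baseline, this route to bias is closed.

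The one figure that stands is the resolution of the baseline comparison, about 0.30 SD either way with 87 per arm. The conclusion assumes that *the researchers* includes at least some of those who screen, recruit, enrol or measure, and that no safeguard stands in material outside the public text.

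**What to change.** **For any assignment still to be made**, replace the access sentence in Statistical Considerations, question 1, with:

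> The Virginia Tech statistician who generates the list holds it. Staff who screen, recruit, enrol or take baseline measurements have no access to upcoming assignments. Each assignment is released only after eligibility, consent and baseline height and weight are recorded.

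Keep simple randomization.

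**For families already assigned**, make no retroactive claim that access was barred. State in the report, for each cohort, who could see the list and whether assignments were released before or after consent and baseline measurement. Where no record exists, say so. Present the baseline comparison already planned, and note its half-width of about 0.30 SD so that a clean table is not read as proof of concealment. If the manual of procedures already holds a safeguard, citing it is enough.

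No extra adjusted model is needed. Statistical Considerations, question 4, already provides for covariates and for exploratory interactions of race, gender and health literacy with time and group. No such model can detect steering on unmeasured factors such as motivation.

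**Cost:** a records check, one paragraph in the report and, if any assignment remains, the handling of its release. No new data are needed from families. Access may be hard to reconstruct for cohort 1, planned from 6/2017.
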